10.3.6 Minimal Residual Disease (MRD) Response Rates

The proportion of subjects achieved 1) CR + CRi and MRD response 2) CR + CRh and MRD response will be calculated among all subjects in the full analysis. The MRD response will be defined using a threshold of less than 10^{-3} of residual blasts per leukocytes as measured in bone marrow. Subjects who are randomized but have no MRD assessment will be considered as non-responders for the calculation of MRD response rate. All subjects in the full analysis set will be included in the analysis.

The proportion of subjects who achieved CR + CRi and MRD response or CR + CRh and MRD response will be compared between two arms using CMH test stratified by age ($18 < 75, \geq 75$) and AML status (de novo, secondary). In addition, 95% confidence interval based on the binomial distribution (Clopper-Pearson exact method) by treatment arms will be provided. The risk difference and 95% confidence interval for the risk difference (exact unconditional confidence limits) will also be provided.

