- End of Cycle 1 (must be performed within ± 3 days of Cycle 1 Day 28 and resulted prior to the administration of treatment for Cycle 2).
- For subjects with resistant disease at end of Cycle 1 a repeat bone marrow must be performed at the end of Cycle 2 or Cycle 3 based on the hematologic recovery to assess for a response of CR/CRi.

- For subjects with a response of CRi on two successive bone marrow samples, an additional bone marrow aspirate and biopsy must be performed to confirm a CR once peripheral blood count recovery is noted. This is not required for subjects who are unblinded following the final analysis results.
- For all subjects a bone marrow aspirate and biopsy must be performed at end of Cycle 4 and every 3 cycles (\pm 1 week) thereafter. This is not required for subjects who are unblinded following the final analysis results. Bone marrow aspirate and/or biopsy can be completed as per institutional standard of care.
- Upon concern for relapse or progressive disease.
- Final Visit (if no BM collected within the last 6 – 8 weeks. Disease assessment is not required if relapse of disease has already been confirmed.)

A bone marrow aspirate and biopsy must be performed for all subjects during screening to confirm diagnosis and to collect mandatory samples for mandatory biomarker assessments. Historical bone marrow aspirates and biopsies assessed locally to confirm the diagnosis may be used as baseline assessment to satisfy eligibility criteria if they were collected as standard of care within 30 days prior to randomization. During screening, after informed consent is signed, bone marrow aspirates and biopsies may be collected to confirm the diagnosis to satisfy eligibility criteria.

During screening, after informed consent is signed, a bone marrow aspirate must be performed for all subjects to collect samples for mandatory biomarker assessments (*biomarker collections are not applicable to subjects enrolled in China*).

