Subjects will be provided with venetoclax/placebo self-administration instructions. Subjects will be instructed to store venetoclax/placebo according to specific directions included in Section 5.5.2.2. Subjects are required to return bottles of venetoclax/placebo (empty, partially filled, or full) to the study site prior to the start of the next cycle and at the Final Visit.

Dispensing LDAC

The IRT will assign every vial of LDAC which was supplied by AbbVie to be dispensed for use by the site. Prior to each drug dispensation, site personnel must contact the IRT for vial number assignment. **AbbVie supplied LDAC cannot be dispensed without contacting the IRT.** AbbVie or designee (refer to Section 7.0) will provide specific instructions on the use of the IRT. LDAC which is to be supplied locally will be dispensed and tracked per the normal practices of those sites.

5.3.1.2 Collection and Handling of Biomarker and Exploratory Research Samples (Not Applicable for China)

Mandatory biospecimens (e.g., blood, plasma, bone marrow aspirate, and bone marrow core biopsy tissue) will be collected per Appendix D. Subjects will also have the option to provide samples for additional exploratory research. Subjects may still participate in the main study even if they decide not to participate in the optional exploratory research. Samples may be utilized to evaluate known and/or novel markers (nucleic acids, peptides/proteins and/or metabolites) of disease status, related conditions or to evaluate the association with pharmacokinetics, safety or efficacy. All samples should be prepared, labeled, and shipped as outlined in the study-specific laboratory manual. The biomarker rationale is discussed in the Biomarker Research Variables Section (Section 5.3.6).

AbbVie (or people or companies working with AbbVie) will store the mandatory and optional biomarker and exploratory research samples in a secure storage space with adequate measures to protect confidentiality. The samples will be retained while research on venetoclax (or drugs of this class) or this disease and related conditions continues, but for no longer than 20 years after study completion. The procedure for obtaining and documenting informed consent is discussed in Section 9.3.

Mandatory Samples for Biomarker Analysis

Blood Collections:

Whole blood will be collected into appropriately labeled tubes and processed as outlined in the most current version of Study M16-043 Laboratory Manual.

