Blood Collection for Plasma:

Approximately 4 mL or 20 mL of blood will be collected prior to dose at:

- Screening visit (4 mL)
- End of Cycle 1 (20 mL)
- Response assessments: every 3 cycles after end of Cycle 1 assessment (20 mL). For subjects who are unblinded following the final analysis results, sample collection every 3 cycles after end of Cycle 1 visit is not required.
- Final Visit/Time of Relapse (20 mL)

Bone Marrow Aspirate and Biopsy Collections

Bone marrow aspirates should be drawn into appropriately labeled tubes in conjunction with the disease assessments. A portion of the aspirate must be processed according to the institutional standard procedures for diagnostic evaluation (locally); however, approximately 6 to 8 mL of the bone marrow aspirate should be collected for biomarker assessments to be shipped to the central laboratory. For subjects, where bone marrow aspirates are no longer required for response assessments, the bone marrow biomarker samples will also not be collected at those timepoints, but the peripheral blood biomarker

samples will be collected. For subjects who are unblinded following the final analysis results, peripheral blood biomarker sample collection every 3 cycles after end of Cycle 1 visit is not required. Detailed processing will be outlined in the most current version of the Study M16-043 Laboratory Manual for the following:

Bone Marrow Collection for Disease Assessment by Flow Cytometry

NOTE: This specimen will be used for detection of residual blasts (i.e., MRD) at the response assessments and should be the first tube drawn from the bone marrow aspirate collection.

Approximately 1 to 2 mL of bone marrow aspirate at:

- Screening visit
- Response Assessments: End of Cycle 1 and every 3 Cycles after end of Cycle 1 visit. For subjects who are unblinded following the final analysis results, sample collection every 3 cycles after end of Cycle 1 visit is not required. Bone marrow aspirate completed as per institutional standard of care should continue to split for this assessment.
- Final Visit/Time of Relapse

Bone Marrow Collection for AML Mutational Profiling

Approximately 1 mL of bone marrow aspirate at:

- Screening visit
- Final Visit/Time of Relapse

Bone Marrow Collection for Translational Research:

Bone marrow aspirate will be collected at:

- Screening visit (4 mL)

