 - $> 50\%$ increase in marrow blasts over baseline (a minimum 15% point increase is required in cases with $< 30\%$ blasts at baseline; or persistent marrow blast percentage of $> 70\%$ over at least 3 months; without at least a 100% improvement in ANC to an absolute level ($> 0.5 \times 10^9/\text{L}$ [500/ μL], and/or platelet count to $> 50 \times 10^9/\text{L}$ [50000/ μL] non-transfused); or
 - 50% increase in peripheral blasts ($\text{WBC} \times \% \text{ blasts}$) to $> 25 \times 10^9/\text{L}$ ($> 25000/\mu\text{L}$); or
 - New extramedullary disease

Reporting of Results

All dosed subjects will be assessed for response to treatment based on the published guidelines. Assessments will be performed at the end of Cycle 1 and every 3 cycles thereafter for response assessment. For subjects who are unblinded following the final analysis results, assessments every 3 cycles thereafter are not required. Bone marrow collection can be completed as per institutional standard of care. Subject will be assigned to one or more of the following categories by investigators:

1. complete remission;

2. complete remission with incomplete blood count recovery;
3. partial remission;
4. morphologic leukemia free state;
5. resistant disease;
6. progressive disease;
7. indeterminate (not assessable, insufficient data);
8. morphologic relapse;

MRD status if performed at investigator sites for subjects who achieve CR or CRi:

1. minimal residual disease negative;
2. minimal residual disease positive.

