The proportion of subjects achieving CR + CRi and MRD or CR + CRh and MRD response status may be calculated. All randomized subjects will be included in the analyses. Subjects who are randomized but have no MRD assessment will be considered as non-negative for the calculation of MRD response status. MRD response will be defined using a threshold of less than 10^{-3} of residual blasts per leukocytes as measured in bone marrow. The MRD response rates may be compared between treatment arms using CMH test stratified by AML status (secondary, de novo) and age ($18 < 75, \geq 75$). In addition, 95% confidence interval will be constructed.

The response rates (e.g., CR + CRi, CR + CRh, or CR) and overall survival in molecular subgroups (e.g., IDH1/2, FLT3) may be evaluated.

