8.2 Demographic and Baseline Characteristics

All baseline characteristic summary statistics and analyses are based on characteristics prior to the first dose of study drug or date of randomization for non-treated subjects.

Distributions of the continuous demographic and baseline characteristic variables will be summarized by treatment arm with the number of non-missing observations, mean, standard deviation, and median, as well as the minimum and maximum values.

For the categorical demographic and baseline characteristic variables, the frequency and percentages of subjects within each category will be summarized by treatment arm. The number of subjects with missing information will also be summarized.

There will be no statistical comparison for the demographic and baseline characteristics between the two treatment arms.

The following demographic and baseline characteristics will be summarized:

Demographics:

- age (years) and age categories (18 – < 75 years, ≥ 75 years)
- gender (male/female)
- race (white, black or African American, Asian, and other)
- region (US, EU, China, JP, and ROW)
- height (cm)

- weight (kg)

Baseline and Disease-Related Characteristics:

- ECOG performance status (0, 1, 2, 3)
- AML Status (de novo, secondary)
- Type of secondary AML (therapy related, post MDS/CMML)
- AML with myelodysplasia related changes (AML-MRC) (Yes, No)
- Cytogenetics risk (favorable, intermediate, poor)
- Bone marrow blast count (< 30%, ≥ 30% – < 50%, ≥ 50%)
- Bone marrow blast count (%)
- CTC grade of neutropenia
- Neutrophils value ($\times 10^9/L$)
- CTC grade of anemia
- Hemoglobin value (G/L)
- CTC grade of thrombocytopenia
- Platelet count ($\times 10^9/L$)
- Reasons for being not eligible for standard induction therapy
- Prior HMA used (Yes, No)
- Antecedent hematologic history of MDS (Yes, No)
- Baseline RBC transfusion dependence (Yes, No)
- Baseline platelet transfusion dependence (Yes, No)
- Molecular marker via central lab (FLT3, IDH1/2, TP53, NPM1)
- Hepatic impairment (Yes, No)
- Renal impairment (Yes, No)

The cross tabulation of the following demographic and baseline characteristics captured in IVRS/IWRS and CRF will be generated:

- Age categories (18 – < 75, ≥ 75 years)
- AML status (de novo, secondary)

- Cytogenetics risk (favorable, intermediate, poor)
- Region (US, EU, China, JP, and ROW)

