10.7 Handling of Multiplicity

The fixed sequence testing procedure will be performed with a significance level of 0.05 for the primary endpoint OS and key secondary efficacy endpoints sequentially. If statistical test is not significant for the primary efficacy endpoint of OS, then statistical significance will not be declared for any of the secondary efficacy endpoints. The Lan-DeMets alpha spending function with O'Brien-Fleming boundary will be used at the interim and final analysis to ensure that the false positive rate for each primary or key secondary efficacy endpoint is 0.05 or less.

For CR + CRi rate, CR + CRi rate by the initiation of Cycle 2, CR + CRh rate, CR + CRh rate by the initiation of Cycle 2, CR rate, transfusion independence rates, and MRD response rate, the information fraction to be used at IA (100 death events) is calculated as detailed in [Table 6](#).

Table 6. Calculation of Information Fraction (IF)

Endpoint	Information Fraction
CR + CRi rate	Portion of subjects with at least 6 months follow up since randomization
CR + CRh rate	Portion of subjects with at least 6 months follow up since randomization
MRD response rate	Portion of subjects with at least 6 months follow up since randomization
CR + CRi rate by the initiation of Cycle 2	Portion of subjects who started Cycle 2 Day 1 dosing or discontinued treatment by the end of Cycle 1
CR + CRh rate by the initiation of Cycle 2	Portion of subjects who started Cycle 2 Day 1 dosing or discontinued treatment by the end of Cycle 1
CR rate	Portion of subjects with at least 9 months follow up since randomization
Transfusion independence rates (RBC/Platelet)	Portion of subjects with at least 9 months follow up since randomization

Table 7 (for EU and EU reference countries) and Table 8 (for US and US reference countries) present the hierarchical ranking and alpha spending for each ranked primary and secondary endpoints at IA and FA.

Table 7. Alpha-spending Boundary (One-sided p-value) for Each Ranked Endpoint for EU and EU Reference Countries

Endpoint		Timing of Analysis	
		IA	FA
1	OS	As specified in Table 2	As specified in Table 2
2	CR + CRi rate ^a	To be calculated with IF as specified in Table 6	To be calculated with IF as specified in Table 6
3	Post-baseline platelet transfusion independence ^a	To be calculated with IF as specified in Table 6	To be calculated with IF as specified in Table 6

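### Subjects in China have no scheduled MRD sample but are scored as MRD non-responders, which pulls the ranked MRD rates and their difference toward zero unless local results count

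*SAP*

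**What the plan says.** **Who is analysed.** SAP 5.1 defines the full analysis set as everyone randomised. SAP 5.2 lists China as one of five region strata. SAP 10.3.6 estimates the proportion with remission plus MRD response (residual blasts below 10^-3) in that whole set, with a stratified CMH test and a risk difference with confidence interval.

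**Missing MRD.** SAP 10.3.6: "Subjects who are randomized but have no MRD assessment will be considered as non-responders for the calculation of MRD response rate". Protocol 8.1.4.2 agrees: "Subjects who are randomized but have no MRD assessment will be considered as non-negative for the calculation of MRD response status".

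**Where the MRD sample comes from.** Protocol 5.3.1.2 schedules a marrow aspirate for flow cytometry and says of it: "This specimen will be used for detection of residual blasts (i.e., MRD) at the response assessments". The heading of 5.3.1.2 excludes China. So does the heading of Appendix D, whose table has the matching MRD row. Protocol 5.3.1.1 repeats that "biomarker collections are not applicable to subjects enrolled in China".

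**Local MRD.** Protocol 5.3.3 lists, among the investigator-reported results, "MRD status if performed at investigator sites for subjects who achieve CR or CRi". Protocol 5.3.1.1 says only that MRD status may be determined. SAP 10.3.6 names no source for the MRD result, although SAP 8.2 does so for mutations: "Molecular marker via central lab".

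**Ranking.** MRD with CR + CRi is rank 8 in SAP Table 7. MRD with CR + CRh and MRD with CR + CRi are ranks 9 and 10 in Table 8.

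**The concern.** Scoring a missing result as non-response is a sensible rule when results go missing incidentally. Here the missingness is built into the sampling plan and is fixed by region before treatment starts. A China subject without remission is scored correctly. A China subject who would have shown remission with MRD response cannot be counted as a success from the scheduled samples.

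The reported rates and risk difference would then depend partly on how many subjects China contributed, and a reader could not separate that from the treatment effect. SAP 12.0 makes a China-specific provision for pharmacokinetics, but there is none for MRD. Neither 10.3.6 nor the additional analyses in 10.6 address the unsampled region.

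**Working it through.** **Inputs.** From the documents: about 140 and 70 subjects per arm (SAP 4.3), the scoring rule (SAP 10.3.6) and the absence of a scheduled MRD sample in China (protocol 5.3.1.2, Appendix D). The documents give no China share, no MRD rates and no planned figure for this endpoint, so there is no figure of the plan's own to reproduce. Assumed: true rates of 15% (venetoclax) and 3% (placebo), a China share s of 5% to 20%, and no local MRD results used.

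**Formulas.** With China shares sV and sP by arm and the same true rates in every region:

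- expected observed rate = p × (1 − s)
- expected difference = 0.15 × (1 − sV) − 0.03 × (1 − sP)
- expected misclassified subjects = n × s × p

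Example at s = 10%: 0.15 × 0.90 − 0.03 × 0.90 = 0.135 − 0.027 = 0.108. Misclassified: 140 × 0.10 × 0.15 = 2.1 and 70 × 0.10 × 0.03 = 0.2.

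| s, both arms | Difference (true 12.0 points) | Misclassified, venetoclax | Misclassified, placebo | Power, full set | Power, sampled regions only |
|---|---|---|---|---|---|
| 5% | 11.4 | 1.1 | 0.1 | 76.9% | 77.2% |
| 10% | 10.8 | 2.1 | 0.2 | 73.9% | 74.6% |
| 15% | 10.2 | 3.2 | 0.3 | 70.7% | 71.7% |
| 20% | 9.6 | 4.2 | 0.4 | 67.2% | 68.5% |

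Power is the unstratified two-proportion normal approximation at two-sided 0.05. If everyone were sampled it would be 79.7%. Exact enumeration of the gap between the last two columns gives −1.1 to +2.4 points, partly from discreteness, so no firm power gain should be claimed for restriction.

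**Other assumed rates.** At s = 10%, 10% vs 2% goes from 8.0 to 7.2 points, 20% vs 5% from 15.0 to 13.5, and 30% vs 5% from 25.0 to 22.5.

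**Unequal shares.** With 8% of venetoclax and 12% of placebo subjects in China: 0.15 × 0.92 − 0.03 × 0.88 = 0.1116. With 12% and 8%: 0.15 × 0.88 − 0.03 × 0.92 = 0.1044. A large imbalance can cancel the shrinkage: for 20% vs 5% with shares of 5% and 20%, 0.20 × 0.95 − 0.05 × 0.80 = 0.150. Stratifying randomisation by region makes such an imbalance unlikely.

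**Type I error.** Under equal true rates, exact enumeration of the full-set test gives 0.042 to 0.049 for null rates of 5% to 15% and s from 0 to 20%. There is no inflation.

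**Is the restricted estimate better?** Let China's true rates be k times those elsewhere in both arms. Against the all-region difference, the full-set estimate is off by −s × k × 12 points and the restricted estimate by +s × (1 − k) × 12. At s = 10%:

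| k | Full set | Sampled regions only |
|---|---|---|
| 0.5 | −0.6 | +0.6 |
| 1 | −1.2 | 0 |
| 1.5 | −1.8 | −0.6 |

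The restricted estimate is closer whenever k exceeds 0.5.

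**The case against.** **Local results may fill the gap.** The SAP rule refers to any MRD assessment, not a central one, and protocol 5.3.1.1 and 5.3.3 leave room for local MRD in China. This stands as a condition on the finding. But local testing is optional, 5.3.3 records it only as positive or negative while the endpoint uses a numerical threshold, and the SAP does not say whether it counts.

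**The rule is deliberate.** Both documents define the endpoint over all randomised subjects, and the other response endpoints treat subjects with no disease assessment the same way. Bias exists only against the rate that would be seen if everyone had been sampled. That is why the ranked analysis should stay as it is. The other response endpoints, however, do not have a whole region without a scheduled assessment.

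**The effect is small.** At 15% vs 3%, the standard error of the difference is √(0.15 × 0.85/140 + 0.03 × 0.97/70) = 3.6 points, so the 95% half-width is about 7.1 points. The 1.2-point shift at s = 10% is about one-sixth of that. This is correct and limits the importance of the point.

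**The test is affected too.** Power does fall as s rises, and under fixed-sequence testing a failure here blocks the endpoints ranked below. Most of that loss comes from the unsampled subjects themselves: in the normal approximation the scoring rule accounts for only 0.3 to 1.3 points.

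**Regional subgroups are already planned.** SAP 10.8 lists China as a separate region and its endpoint list is open-ended. It does not name MRD and does not define a comparison limited to sampled regions.

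**Conclusion.** The concern holds, on the stated condition that local MRD results are not used. Applied as written, the rule lowers the MRD rates and their difference by a factor of about 1 − s: 0.6 to 2.4 points off an assumed 12.0-point difference for s between 5% and 20%, or roughly one to four venetoclax subjects and fewer than one placebo subject. This rests on assumed rates and China shares, similar shares by arm and similar true rates across regions. The direction holds for any China share above zero when shares are similar by arm.

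The bias is conservative. Type I error is not inflated, and with equal shares the ratio of the two rates is unchanged. This is an estimation problem in lower-ranked endpoints that should be corrected; it does not threaten the trial's main conclusions.

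**What to change.** 1. State in SAP 10.3.6 whether the MRD result is central only or central plus local. If local results count, say how a positive or negative report is mapped to the 10^-3 threshold.
2. Keep the full-analysis-set analysis as the ranked one. Beside it, specify the same rates, risk difference and stratified CMH test among randomised subjects in regions where MRD samples are collected, with missing scored as non-response within that set. Because randomisation is stratified by region, this remains a randomised comparison.
3. Report by arm the number of China subjects and how many reached CR + CRi or CR + CRh without an MRD result.

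**Cost.** A short SAP addition and one more table, with no protocol change and no change to the ranking or alpha. The restricted estimate applies only to the sampled regions and has a smaller denominator: 210 × 0.90 = 189 at an assumed s = 10%. If the sponsor instead made it the ranked analysis, protocol 8.1.4.2 and the MRD information fraction in SAP Table 6 would both have to be changed to match.

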10.3.7 Quality of Life (QoL)

Any subject who does not have baseline measurement or any post-baseline measurements in the full analysis set will not be included in QoL analyses. Post-baseline measurements will be obtained according to the visit window as in [Table 3](#).

PROMIS Cancer Fatigue SF 7a

PROMIS instruments measure concepts such as pain, fatigue, physical function, depression, anxiety and social function.

(<https://www.assessmentcenter.net/documents/PROMIS%20Fatigue%20Scoring%20Manual.pdf>). Fatigue will be assessed using the PROMIS Cancer Fatigue SF that has been

developed for use in oncology populations. PROMIS Cancer Fatigue SF 7a is a seven item questionnaire that assesses the impact and experience of fatigue over the past 7 days. All questions employ the following five response options: 1 = Never, 2 = Rarely, 3 = Sometimes, 4 = Often, and 5 = Always.

Scores will be computed according to the procedures outlined in the PROMIS Fatigue scoring manual, available at <https://www.assessmentcenter.net/Manuals.aspx>. A linear mixed effects regression model with an appropriate covariance structure will be fitted to the longitudinal data to test for differences between the two treatment arms. For the linear mixed effects regression model, stratification factors (age (18 – < 75, ≥ 75) and AML status (de novo, secondary)) and treatment arm will be included as fixed factors. Furthermore, time and treatment by time interaction will be included in the model. The repeated correlation structure in the timepoints will be assessed by using the Bayesian Information Criterion (BIC). The following covariance structures will be explored: Unstructured (TYPE = UN), compound symmetry (TYPE = CS) and first-order autoregressive (TYPE = AR(1)). The type resulting in model convergence and the lowest BIC will be used for analysis. Change in the PROMIS Fatigue score from baseline will be compared between the two treatment arms for each post baseline visit except the final observation.

EORTC QLQ-C30

The QLQ-C30 is a 30-item subject self-report questionnaire composed of both multi-item and single scales, including five functional scales (physical, role, emotional, social, and cognitive), three symptom scales (fatigue, nausea and vomiting, and pain), a global health status/quality of life scale, and six single items (dyspnea, insomnia, appetite loss, constipation, diarrhea, and financial difficulties). Subjects' rate items on a four-point scale, with 1 as "not at all" and 4 as "very much."

Scores will be computed according to procedures outlined in the EORTC QLQ-C30 scoring manual, available at <http://groups.eortc.be/qol/manuals>. A linear mixed effects regression model with an appropriate covariance structure will be fitted to the longitudinal

data to test for differences between the two treatment arms. For the linear mixed effects regression model, stratification factors (age ($18 < 75, \geq 75$) and AML status (de novo, secondary)) and treatment group will be included as fixed factors. Furthermore, time and treatment by time interaction will be included in the model. The repeated correlation structure in the timepoints will be assessed by using the Bayesian Information Criterion (BIC). The following covariance structures will be explored: Unstructured (TYPE = UN), compound symmetry (TYPE = CS) and first-order autoregressive (TYPE = AR(1)). The type resulting in model convergence and the lowest BIC will be used for analysis. Change in the PROMIS Fatigue score from baseline will be compared between the two treatment arms for each post baseline visit except the final observation.

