4	CR + CRi rate in IDH1/2 subgroup ^{a,b}	To be calculated with IF as specified in Table 6	To be calculated with IF as specified in Table 6
5	CR rate ^a	To be calculated with IF as specified in Table 6	To be calculated with IF as specified in Table 6
6	CR + CRi by the initiation of Cycle 2 ^a	To be calculated with IF as specified in Table 6	To be calculated with IF as specified in Table 6
7	Post-baseline RBC transfusion independence ^a	To be calculated with IF as specified in Table 6	To be calculated with IF as specified in Table 6
8	MRD and CR + CRi response rate ^a	To be calculated with IF as specified in Table 6	To be calculated with IF as specified in Table 6
9	EORTC QLQ-C30	0.0001	0.025
10	PROMIS Cancer Fatigue SF 7a	0.0001	0.025
11	OS in IDH1/2 subgroup ^b	0.0001	0.025
12	OS in FLT3 subgroup ^b	0.0001	0.025
13	CR + CRi rate in FLT3 subgroup ^b	0.0001	0.025
14	EFS	0.0001	0.025

- a. The Lan DeMets with O'Brien-Fleming approach will be applied to determine the efficacy boundaries of the following ranked secondary endpoints with the information fraction define in Table 6.
- b. If the size of identified subgroup population is less than 30 or randomization ratio between Venetoclax + LDAC arm and placebo + LDAC arm is higher than 3:1 at the time of IA and FA, the endpoint will be ranked below EFS in the fixed sequence testing procedure.

Table 8. Alpha-spending Boundary (One-sided p-value) for Each Ranked Endpoint for US and US Reference Countries

Endpoint		Timing of Analysis	
		IA	FA
1	OS	As specified in Table 2	As specified in Table 2
2	CR + CRh rate ^a	To be calculated with IF as specified in Table 6	To be calculated with IF as specified in Table 6
3.	CR + CRi rate ^a	To be calculated with IF as specified in Table 6	To be calculated with IF as specified in Table 6
4	Post-baseline platelet transfusion independence ^a	To be calculated with IF as specified in Table 6	To be calculated with IF as specified in Table 6
5	CR + CRh rate in IDH1/2 subgroup ^{a,b}	To be calculated with IF as specified in Table 6	To be calculated with IF as specified in Table 6
6	CR rate ^a	To be calculated with IF as specified in Table 6	To be calculated with IF as specified in Table 6
7	CR + CRh by the initiation of Cycle 2 ^a	To be calculated with IF as specified in Table 6	To be calculated with IF as specified in Table 6
8	Post-baseline RBC transfusion independence ^a	To be calculated with IF as specified in Table 6	To be calculated with IF as specified in Table 6

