9	MRD and CR + CRh response rate ^a	To be calculated with IF as specified in Table 6	To be calculated with IF as specified in Table 6
10	MRD and CR + CRi response rate ^a	To be calculated with IF as specified in Table 6	To be calculated with IF as specified in Table 6
11	PROMIS Cancer Fatigue SF 7a	0.0001	0.025
12	EORTC QLQ-C30	0.0001	0.025
13	OS in IDH1/2 subgroup ^b	0.0001	0.025
14	OS in FLT3 subgroup ^b	0.0001	0.025
15	CR + CRh rate in FLT3 subgroup ^b	0.0001	0.025
16	EFS	0.0001	0.025

- a. The Lan DeMets with O'Brien-Fleming approach will be applied to determine the efficacy boundaries of the following ranked secondary endpoints with the information fraction define in Table 6.
- b. If the size of identified subgroup population is less than 30 or randomization ratio between Ven + LDAC arm and placebo + LDAC arm is higher than 3:1 at the time of IA and FA, the endpoint will be ranked below EFS in the fixed sequence testing procedure.

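### SAP 10.3.7 omits the baseline score from the PRO mixed models, closes the EORTC paragraph with the PROMIS score, and does not say which contrast decides each ranked PRO row

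*SAP*

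**What the plan says.** SAP 10.3.7 limits the PRO analyses by baseline availability: "Any subject who does not have baseline measurement or any post-baseline measurements in the full analysis set will not be included in QoL analyses". For both instruments it then describes a linear mixed model that "will be fitted to the longitudinal data to test for differences between the two treatment arms". The fixed terms are age group, AML status and arm, after which "time and treatment by time interaction will be included in the model". The covariance structure is chosen by BIC. The baseline score is not listed, and the text does not say whether the response is the raw score or the change from baseline.

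The PROMIS paragraph closes with: "Change in the PROMIS Fatigue score from baseline will be compared between the two treatment arms for each post baseline visit except the final observation". The EORTC QLQ-C30 paragraph closes with the identical sentence. It describes the questionnaire's many scales but does not say which one is ranked. SAP 4.1 and protocol 8.1.4.2 both name GHS/QoL.

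SAP 10.7 ranks the two PROs in Table 7 ("Alpha-spending Boundary (One-sided p-value) for Each Ranked Endpoint for EU and EU Reference Countries"), with EORTC at 9 and PROMIS at 10, and in Table 8 ("Alpha-spending Boundary (One-sided p-value) for Each Ranked Endpoint for US and US Reference Countries"), with "PROMIS Cancer Fatigue SF 7a" at 11 and EORTC at 12. Each row has one boundary: 0.0001 at the interim and 0.025 at the final analysis. No visit, average or model term is named.

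**The concern.** There are three gaps of unequal weight.

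- **Baseline.** A covariate that every analysed subject has is left out, so precision is given up for nothing.
- **Copied sentence.** Within 10.3.7, the by-visit comparison in the EORTC paragraph is of the wrong instrument. Programmed literally, it repeats the PROMIS analysis.
- **Deciding contrast.** Each PRO row needs one p-value to set against its boundary, and the SAP does not say which. Two statisticians could decide the same row differently.

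The third gap is the one with confirmatory consequences. OS in the IDH1/2 and FLT3 subgroups, response in FLT3, and EFS all sit below the PRO rows and open only through them. The IDH1/2 response row joins them if it is small or unbalanced, since then "the endpoint will be ranked below EFS in the fixed sequence testing procedure".

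**Working it through.** The plan states no power, standard deviation or correlation for either PRO, so there is no PRO figure to reproduce. The correlation rho between baseline and visit scores (equal variances) is an assumption, shown from 0.3 to 0.7.

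**1. Single visit, complete data, compound symmetry.** Variances are in units of the score variance.
- Change score, no baseline covariate: 2(1 − rho).
- Raw score, no baseline covariate: 1.
- Either response with the baseline covariate: 1 − rho².

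| rho | Adjusted / change = (1 + rho)/2 | Reduction | Adjusted / raw = 1 − rho² | Reduction |
|---|---|---|---|---|
| 0.3 | 0.65 | 35% | 0.91 | 9% |
| 0.5 | 0.75 | 25% | 0.75 | 25% |
| 0.7 | 0.85 | 15% | 0.51 | 49% |

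The two readings run in opposite directions: the gain is larger at low correlation for change and at high correlation for the raw score.

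**2. Average over Cycles 3, 5 and 7, complete data, response change.** With v = (1 + 2rho)/3, the ratio is (v − rho²)/(v + 1 − 2rho) = 0.475, 0.625, 0.775 at rho 0.3, 0.5, 0.7, a reduction of 22-52%.

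**3. The same average with attrition.** Inputs are the medians of 6 and 11 months and the 70 and 140 subjects in SAP 4.3. Assume exponential survival and that everyone alive answers. With t = (cycle − 1) × 28/30.4375 months, the shares alive are 0.5^(t/6) and 0.5^(t/11).

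| Cycle | Placebo share (of 70) | Venetoclax share (of 140) |
|---|---|---|
| 3 | 0.809 (57) | 0.891 (125) |
| 5 | 0.654 (46) | 0.793 (111) |
| 7 | 0.529 (37) | 0.706 (99) |

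Generalized least squares with monotone dropout and known compound-symmetry covariance gives:
- Response change: ratios 0.501, 0.646, 0.788 (reduction 21-50%). The standard error in SD units goes from 0.162 to 0.115, 0.137 to 0.110, and 0.106 to 0.094.
- Response raw score: reduction 16-59%.
- Baseline fitted as a time level, with the two arm means at baseline constrained equal: ratios 0.511, 0.653, 0.793, close to the change reading.

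The counts are upper limits on respondents. Protocol 5.3.1.1 and Appendix C schedule PROs on Day 1 of every other cycle and at the Final Visit, with none in post-treatment follow-up. Actual standard errors would therefore be larger.

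**4. What the wording leaves open on the contrast.** A joint arm-by-time test has no sign and cannot be set against a one-sided boundary. An arm effect in a model that also contains arm-by-time has a definite meaning only once the visits and their weights are fixed. SAP 6.0 Table 3 leaves the visit set open-ended from Cycle 3 onward. As illustration only, take three visits, a cutoff of 1.96 and an assumed equal correlation of 0.5 to 0.9 between visit statistics:
- one named contrast: one-sided error 0.025;
- any of the three may win: 0.063 down to 0.042;
- all three must win: 0.002 up to 0.011.

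**The case against.** Much can be said for the plan as written.

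- **Direction is given.** SAP 4.1 says fatigue is to fall and GHS/QoL to improve, and Tables 7 and 8 are one-sided. This stands: the sign is not missing.
- **The model test can be read as the arm effect**, a single signed contrast. That reading is natural, but 10.3.7 does not state it. The by-visit comparisons follow directly without being called secondary, and the visits over which the arm effect is taken are not fixed.
- **A by-visit EORTC comparison exists elsewhere.** SAP 10.4.1 covers all QLQ-C30 scales and PROMIS at each assessment. This stands, but the heading there is exploratory, so it does not settle the ranked row.
- **The PROMIS sentence is a copy error.** Agreed. The intended scale is not in doubt and the correction is editorial.
- **Omitting baseline does not bias a randomized comparison.** Agreed. It is a matter of efficiency, and its size depends on an unstated response variable and an assumed correlation.

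A reader might go further and infer that a win at any visit is enough, so that the error rate of these rows is inflated. The documents do not support that: nothing in the SAP prescribes an any-visit or all-visit rule. The error rates above show how wide the ambiguity is; they are not properties of the plan.

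**Conclusion.** The point holds as a specification gap of limited reach. Baseline is required for inclusion but absent from both models. On the stated assumptions this costs precision that adjustment would recover: 15-35% of single-visit variance if the response is change, 9-49% if it is the raw score. The EORTC sentence names the wrong score. Neither 10.3.7 nor Tables 7 and 8 says which visit, average or model term decides each PRO row; the sign is known, the contrast is not.

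The PRO rows are tested only after OS and every higher-ranked endpoint succeed, so those results are untouched. The consequence falls on the PRO rows and the rows below them.

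**What to change.** For the SAP text:

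1. State that the response is change from baseline at post-baseline visits, and add the baseline score and baseline-by-visit as covariates.
2. In the last sentence of the EORTC paragraph, replace the PROMIS score by the EORTC QLQ-C30 GHS/QoL score. Label the row EORTC QLQ-C30 GHS/QoL in Tables 7 and 8.
3. Name one contrast per PRO row, for example the average arm difference in change over Cycles 3, 5 and 7, with lower fatigue and higher GHS/QoL as the favourable direction. Make by-visit results descriptive, and report the number on treatment and answering per arm and visit, because the contrast describes only those subjects.

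Before unblinding, this costs SAP wording and minor programming, with no new data. However, protocol 1.1 reports that the final efficacy analysis has been performed, so a contrast or covariate chosen now would be post hoc. Report the contrast that was documented before unblinding. If there was none, present the PRO rows and those below them as descriptive. In either case, show the baseline-adjusted model as a sensitivity analysis. That costs reporting wording and one extra run per PRO.
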